4.3.2 Adherence Assessment

During the 28-day intervention phase, all subjects will be contacted on Study Days 3, 6, 9, 14, 15, 21 and 28 via automated REDCap email or SMS text messages via Twilio service. Study Day 28 will only be collected via REDCap email or phone. These points of contact are to collect data about stool frequency and consistency among all subjects and therefore lactulose adherence in the treatment group. If the subject opts out of Twilio service, the subject can also receive these questions via REDCap automated email or a study coordinator will collect this data from the subject directly via phone or email. On Study Days 3, 6, 9, 14, 21 and 28 subjects will be asked the following questions:

1. "How many bowel movements did you have yesterday? Please respond with a whole number." *If 0-4 bowel movements are reported the subject will exit the survey. If >4, the subject will receive the following instructions:*

Since you had > 4 bowel movements yesterday, please reduce to **one** 20g dose of kristalose (1 packet) packet per day. Please call the study line at [contact] if you continue to have more than 4 bowel movements daily or with any questions or concerns.

On Study Day 15 subjects will be asked:

2. "Please reference the Bristol Stool Chart we provided to you to answer this question. How would you describe your stool looks today? Please respond with the applicable number, between 1-7. *All subjects exit survey after response.*

1. Separate hard lumps
2. Sausage-shaped but lumpy
3. Like a sausage but with cracks on its surface
4. Like a sausage or snake, smooth and soft
5. Soft blobs with clear cut edges
6. Fluffy pieces with ragged edges, a mushy stool
7. Watery, no solid pieces, entirely liquid

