**A Randomized Trial to Improve Quality of Life in
People with Cirrhosis – the Mi-Kristal RCT**

IRB Approval Date: December 1, 2021

NCT05061992

**A Randomized Trial to Improve Quality of Life in People with Cirrhosis –
the Mi-Kristal RCT**

Principal Investigator (PI):

[name]

Division of Gastroenterology and Hepatology
Department of Internal Medicine
University of Michigan, Ann Arbor, MI

Correspondence:

[name]

[name]

[name]

P: [contact]

F: [contact]

e: [contact]

Key words: Cirrhosis, Hepatic Encephalopathy, Liver Disease

Disclosures: No conflicts of interest to disclose

SUMMARY

Study Name	A Randomized Trial to Improve Quality of Life in People with Cirrhosis – the Mi-Kristal RCT
Subject Population	At least 50 patients with cirrhosis and portal hypertension, with no previous lactulose use, and moderate to high self-reported daily activity impairment.
Objective	To determine if lactulose therapy improves health-related quality of life (HRQOL), cognitive function, sleep quality and activity level impairment and reduces number of falls.
Design	Randomized two-arm study of lactulose
Arms	Treatment: Crystalized Lactulose (Kristalose) Control: No intervention
Procedures	
- Screen cirrhosis patients and determine if they meet inclusion and exclusion criteria.- Determine regular daily activity level impairment using WPAI; consent and randomize patients.- Collect demographic information and conduct baseline assessments: questionnaires assessing HRQOL, cognitive function, sleep quality, health history and current alcohol use.- Randomized subjects receive 28 days of crystallized lactulose therapy (20g twice daily (b.i.d.)) or no therapy.- Automated SMS or email follow-up at 3, 6, 9, 14, 15, 21 and 28 days with patients in treatment group: assess bowel movements; may be done via email or phone if required.- 28-day follow-up evaluation consists of questionnaires assessing HRQOL, cognitive function, sleep quality, falls and activity level impairment.
Site	Michigan Medicine, Ann Arbor, MI

Table of Contents

SIGNIFICANCE	5
1. STUDY OBJECTIVES	5
1.1 Specific Aims	5
1.1.1 Primary Aims	5
1.1.2 Secondary Aims	5
1.2 End Points	6
2. STUDY DESIGN	6
3. SELECTION AND ENROLLMENT OF SUBJECTS	7
3.1 Inclusion Criteria	7
3.2 Exclusion Criteria.....	7
3.3 Study Enrollment Procedures	8

3.3.1 Identification & Recruitment.....	8
3.3.2 Monitoring of Recruitment Targets	8

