2. STUDY DESIGN

Overview: We propose a randomized two-arm parallel group trial to determine if lactulose therapy in cirrhosis patients with portal hypertension who report moderate to high regular daily activity impairment and have no history of prior lactulose use or HE within 6 months, improves their HRQOL, cognitive function and overall sleep quality at 28 days post-baseline. Subjects will be randomized to one of two groups:

- 1) Treatment: subjects prescribed and instructed to take 20g (dissolved in 4oz of water) dose of lactulose twice daily (upon awakening and then 4 hours later) for 28 days.
- 2) Control: subjects are asked to complete baseline and outcome assessments at 28 days and no intervention or placebo will be prescribed.

Our goal is to have 50 patients with cirrhosis who meet study eligibility criteria (see Section 3 below) complete study participation, with approximately 25 subjects in each arm. We will enroll up to 75 subjects to account for subject withdrawals, lost to follow-up, death, transplant or PI discretion.

Figure 1. Study Design

We will enroll patients with cirrhosis who report impairment of daily activities, defined by scores ≥ 3 on the 0-10 activity impairment scale from the Work-Productivity Activity index and assess the impact of lactulose therapy on health-related quality of life (HRQOL), cognitive function (animal naming test, ANT), sleep quality, and falls

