3. SF-8
4. ANT
5. AUDIT-C

4.3 INTERVENTION PROCEDURES

4.3.1 Lactulose Administration and Duration

Subjects randomized to the control are not required to complete any intervention activities or treatments. For subjects randomized to lactulose therapy, the following steps to implement the intervention will occur on Study Day 1:

1. The Principal Investigator (PI) will prescribe lactulose to subjects enrolled at Michigan Medicine. Lactulose (Kristalose) will be allocated to the patient in person at the University of Michigan through the Investigational Pharmacy. If enrollment procedures were conducted remotely, the patient will be allowed up to two weeks to schedule an appointment with the study coordinator to receive Kristalose.
2. Subjects will be instructed to take 20g of Kristalose (1 packet) in 4oz water twice daily for 28 days. All patients randomized to lactulose will receive standard counselling.
3. First, all subjects will be instructed to take the first dose on awakening and the second dose approximately 4 hours after the first dose.
4. Second, subjects will be asked to monitor their bowel movements (see section 4.3.2 Adherence Assessment below). If they achieve ≥ 4 bowel movements in one day outside of the adherence assessments, they will be asked to contact the study team directly and will be instructed to reduce their lactulose frequency to one 20g dose daily. No dose adjustments will be made to *increase* bowel movements. Study staff will be alerted via email if a subject reports more than 4 bowel movements per day. Subjects will be instructed to call the study phone line if their bowel movements do not decrease with a reduced dose. They will also be instructed to notify the study team if they are undergoing proctoscopy or colonoscopy and to avoid taking nonabsorbable antacids (like aluminum or magnesium hydroxide) with Kristalose since these may interfere with the lactulose activity.
5. Third, patients will be counselled on the side effects of lactulose including mild bloating, cramping or diarrhea. If the symptoms worry the patient, they will be instructed to reduce lactulose to one 10g dose on awakening and then to increase to 10g twice daily as tolerated.

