7.4 USE OF TWILIO SERVICE

We will work with the Michigan Institute for Clinical and Health Research (MICHR) to construct our REDCap database and connect it with Twilio. Twilio (<https://www.twilio.com>) is a third-party service used to send automated SMS messages and phone call surveys to users for a variety of purposes. We will use Twilio to send follow-up communications to subjects in the intervention groups on Study Days 3, 9, 9, 14, 21 and 28. The only piece of information transmitted from our REDCap database to Twilio will be the phone number of the participant. Participants will choose to either opt-in or opt-out of using Twilio service. Participants that choose to opt-in to the service must provide informed consent to use the service and must agree to Twilio's privacy policy and terms of service. All participants who refuse to use the Twilio service will be offered alternative means of follow-up including phone, text, and/or email communications directly sent from the study coordinator. No protected health information (PHI) will be requested from the patients or sent by the study team through Twilio. The only information transmitted through Twilio SMS text messages or phone calls will be non-identifiable responses to questions about the number of times per day the subject has bowel movements.

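### The stool-survey branch in Section 4.3.2 has no arm condition, so as written a control can be told to reduce Kristalose; the Summary instead limits the survey to the treatment group

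*Combined protocol and SAP*

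**What the plan says.** Section 4.3.2 (Adherence Assessment) schedules contacts on Study Days 3, 6, 9, 14, 15, 21 and 28 for every participant. It gives their purpose as "to collect data about stool frequency and consistency among all subjects and therefore lactulose adherence in the treatment group". On six of those days the subject reports the previous day's number of bowel movements. A count of 0 to 4 ends the survey. Above that, the rule is "If >4, the subject will receive the following instructions", and the text sent tells the recipient to go down to one "20g dose of kristalose (1 packet) packet per day". It also gives the study telephone line.

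Other sections describe who is contacted differently:

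- The Summary (Procedures row) lists the same seven days as follow-up at those times and "28 days with patients in treatment group: assess bowel movements".
- Section 7.4 says "We will use Twilio to send follow-up communications to subjects in the intervention groups". It is silent on who gets the REDCap email or telephone versions.
- Section 2 says of controls that "subjects are asked to complete baseline and outcome assessments at 28 days and no intervention or placebo will be prescribed". It does not mention the interim surveys.

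Section 4.3.3 dispenses Kristalose only to subjects randomized to treatment. Aim 5a (Exploratory Adverse Event Aims) compares between arms the self-reported episodes of more than five bowel movements in a day. Section 1.2 separately lists the average number of daily bowel movements at 28 days as a between-group endpoint.

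**The concern.** A message to participants that changes a dose should depend on whether the participant has the drug. Here it depends on the stool count alone. If the survey is built from Section 4.3.2, a control with frequent stools gets an instruction that makes no sense for them, and may be confused or call the study line.

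If it is built from the Summary, that cannot happen, but controls are not asked for daily counts at all. Aim 5a then has an episode count in one arm and nothing to compare it with. A person building the REDCap survey cannot satisfy both sections, and each choice has its own defect. At stake are the clarity of one message and the data for one exploratory aim.

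**Working it through.** The plan states no figure on this point, so the check sets the sections side by side and counts scheduled contacts.

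**Step 1: who are the subjects in 4.3.2?** The phrase alone does not settle it. Section 4.3.1, item 3 says "all subjects will be instructed to take the first dose on awakening", where only the lactulose arm can be meant; that list is introduced as applying to subjects randomized to lactulose. Section 4.3.2 has no such introduction. Its purpose sentence names all subjects for stool data and the treatment group for adherence, as two different sets. So in 4.3.2 the phrase covers both arms. Table 1 does not split the message row by arm, but this is weak support, because its lactulose row is not split either.

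**Step 2: does anything in the branch exclude controls?** No. The only condition is a count above 4. A control reporting 5 meets it and receives the Kristalose text.

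**Step 3: which sections conflict with 4.3.2?**

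| Section | Who is contacted | Status |
|---|---|---|
| 4.3.2 | Both arms | Express |
| Summary | Treatment group | Express conflict |
| 7.4 | Intervention groups | Conflict for Twilio messages only |
| 2 | Not mentioned for controls | Omission, not exclusion |

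**Step 4: daily counts available for Aim 5a.** The count is asked on Days 3, 6, 9, 14, 21 and 28, which is 6 occasions; Day 15 asks about stool form only.

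- Under 4.3.2: up to 6 per subject in each arm. At 25 controls, 6 × 25 = 150 scheduled counts.
- Under the Summary: 0 per control, and up to 6 per treated subject.

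The 150 is a number of scheduled surveys, a ceiling if all are answered. It is not a number of misdirected messages. The documents give no rate of more than four stools a day in controls, so that number is not estimated.

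**Step 5: can other items fill the gap?** Appendix B (item 18, baseline) and Appendix G (item 4, follow-up) both ask for an average per day. An average can show whether a subject's usual frequency exceeds five, but cannot count the days on which it did. For the Section 1.2 endpoint, which is itself an average, these items suffice, and Section 4.4 gives the follow-up questionnaire to all subjects.

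**The case against.** The best case for the plan is that the arm condition sits one section earlier. Dose reduction is described in Section 4.3.1, item 4, among steps for subjects randomized to lactulose, and that item refers forward to 4.3.2. The same section opens by saying that controls have no intervention activities to complete. On that view the message is simply the titration step for the lactulose arm. This shows what was probably intended. It does not supply the missing condition, because 4.3.2 widens the survey to both arms and then triggers the message on the count alone.

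Section 4.3.1 also provides that "Study staff will be alerted via email if a subject reports more than 4 bowel movements per day", so staff could correct a misdirected message, and the message itself gives the study line. Both mitigate the problem. The staff alert is listed among the lactulose-arm steps, though, so the text does not say whether it covers controls.

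It is also fair to say that Aim 5a is thinly served under either reading. Six one-day counts sample at most 6 of 28 days, and neither arm has an episode count at baseline. That stands, and it limits how much the missing control counts would cost.

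A reader might infer that controls could end up taking lactulose. The documents do not support this: controls are prescribed nothing, drug is dispensed only to the treatment group, and an instruction to reduce presupposes a supply. A reader might also infer that Section 2 rules out control surveys. It only fails to mention them.

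**Conclusion.** The point holds as a minor drafting inconsistency with a practical consequence. As written, Section 4.3.2 sends a wrong drug instruction to any control who reports more than four bowel movements. The Summary avoids this only by leaving the control arm with 0 daily counts, against up to 6 per treated subject, for Aim 5a.

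The two defects belong to alternative readings. A reader might infer that the trial suffers both at once, but if controls are surveyed they have counts, and if they are not they get no message. Nor does the Summary's reading leave controls without any bowel data, since the baseline and follow-up averages remain. The Section 1.2 bowel-movement endpoint is unaffected either way, no primary or secondary endpoint changes, and no sample-size or power figure is involved.

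The conclusion concerns the written rule. The REDCap build is not shown, and it may already carry an arm condition or follow the Summary.

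**What to change.** 1. In Section 4.3.2, send the dose-reduction text only to subjects randomized to lactulose, on every route (SMS, REDCap email, coordinator telephone or email). Controls exit after giving the count, or receive neutral text that names no drug and gives the study line.
2. Correct the Summary and Section 7.4 to say that both arms are surveyed, and mention the surveys in the Section 2 description of the control arm.
3. While editing, state in Section 4.3.1 whether the staff alert covers controls, and state which instrument defines Aim 5a.

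If the build already surveys both arms, the cost is one survey condition, the wording edits, and the written IRB-approved amendment that Section 8.4 requires. The data collected do not change. If the build follows the Summary, the fix also adds up to seven brief contacts per control (six counts and the Day 15 stool-form question), and controls who choose SMS need the Twilio opt-in consent described in Section 7.4.

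### The fixed >4-stool message in 4.3.2 names one 20g dose a day whatever the subject is taking; for a subject stepped down to one 10g dose it names twice the current dose (minor patient safety, cheap to fix)

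*Combined protocol and SAP*

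**What the plan says.** Section 4.3.2 collects stool counts by automated message or email: "On Study Days 3, 6, 9, 14, 21 and 28 subjects will be asked the following questions". A count of 0 to 4 ends the survey. For a higher count, "If >4, the subject will receive the following instructions". There is only one such text. It opens "Since you had > 4 bowel movements yesterday, please reduce to", names one "20g dose of kristalose (1 packet) packet per day", and ends by asking the subject to ring the study line if counts above 4 persist or if there are questions. The survey does not ask what dose is being taken.

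Section 4.3.1 sets the doses. Item 2 assigns 20g twice daily. Item 4 has a parallel rule outside the surveys: a subject with four or more stools in a day contacts the team and is cut to one 20g dose daily, again with no condition on current dose. Item 4 also provides two safeguards: "Study staff will be alerted via email if a subject reports more than 4 bowel movements per day" and "Subjects will be instructed to call the study phone line if their bowel movements do not decrease with a reduced dose". Item 5 introduces lower doses. It says that "patients will be counselled on the side effects of lactulose including mild bloating, cramping or diarrhea". For anyone troubled by such effects it then sets this step-down: "they will be instructed to reduce lactulose to one 10g dose on awakening and then to increase to 10g twice daily as tolerated".

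Section 4.3.3 describes only 20g packets being dispensed. On who is contacted, 4.3.2 says all subjects, whereas the Summary and 7.4 describe the contacts as going to the treatment or intervention group.

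**The concern.** Diarrhea is one of the named reasons for stepping down to 10g, and a count above 4 is what triggers the message. The same complaint can therefore put a subject on the lower dose and then bring the message. Since the message names one packet, and 20g packets are what the protocol describes the subject receiving, a subject who simply follows it would go from half a packet to a whole one just after reporting more than 4 stools. Item 5 reaches 20g a day only as tolerated and in two split doses; the message names it in one dose.

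At stake is a small, avoidable safety risk. Section 8.3 lists diarrhea, dehydration and, rarely, sodium or potassium disturbance among the risks of lactulose.

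**Working it through.** The check compares the daily dose named in the message with each daily dose the protocol allows.

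**Inputs**
- Dose in the message (4.3.2): 1 packet × 20g = 20g a day.
- Assigned dose (4.3.1 item 2): 2 × 20g = 40g a day.
- Dose after the stool-count rule (4.3.1 item 4, or an earlier survey message): 1 × 20g = 20g a day.
- Doses after a side-effect step-down (4.3.1 item 5): 1 × 10g = 10g a day, then 2 × 10g = 20g a day as tolerated.

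**The plan's own case.** From the assigned dose, 20/40 = 0.5. The message halves the dose, as it is meant to.

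**All stated doses.** Ratio = dose in message / current daily dose.

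| Current regimen | Current daily dose | Dose in message | Ratio | Effect if followed |
|---|---|---|---|---|
| 20g twice daily | 40g | 20g | 0.5 | Halved |
| One 20g packet | 20g | 20g | 1.0 | No change |
| 10g twice daily | 20g | 20g | 1.0 | No change in daily total |
| One 10g dose | 10g | 20g | 2.0 | Doubled (+10g) |

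A pause is also possible: 4.6 allows lactulose to be paused or discontinued when a hospitalization results from an adverse event of the drug. The message would then name 20g when no dose is intended. This is a rarer case, and the PI is already involved in it.

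**Does any text exempt the 10g subject?** The survey in 4.3.2 splits on stool count alone. Item 5 does not mention the message. The staff alert in item 4 is not said to include a dose check or to override the message. No exemption is stated.

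**Upper limit.** The highest daily dose that following the message can produce is 20g, and 20/40 = 0.5 of the assigned dose.

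**Control arm.** Read literally, 4.3.2 surveys controls and branches only on stool count, so a control reporting more than 4 stools would receive a dosing instruction for a drug they do not have. The Summary and 7.4 point the other way. The text should settle this.

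**The case against.** The strongest reply is that the intent is plain. Item 4 describes the same action as a cut in frequency, from twice to once daily, and rules out dose changes aimed at producing more stools. The message says reduce, so a subject on 10g would have to read that word as an instruction to double. The message carries a call line, and staff are emailed. Every treated subject starts at 40g, where the message is right. The two no-change regimens are not harmful in themselves, since the subject is told to call if high counts continue. The doubling also ends once the subject moves up to 10g twice daily, as item 5 directs when tolerated.

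Most of this stands, and it limits the size of the point. It does not correct the text: the message gives the dose before it offers the call line, and for a subject on 10g the sentence contradicts itself.

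It can also be argued that staff would know who has stepped down. Item 5 can be read as counselling given in advance on Study Day 1, in which case a subject could step down unannounced, or as an instruction given when a subject reports worry, in which case staff know the dose. The text does not settle which, so it cannot be assumed either that step-downs go unreported or that staff would catch the mismatch.

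A reader might infer that the message misdirects lactulose subjects generally, because it lowers the dose in only one of the four regimens. That would count regimens, not people. A reader might also count the surveys remaining after an early step-down and treat the number as a frequency. Each message needs more than 4 stools the day before, and the doubling needs the subject still to be on one 10g dose. The documents give no rate for either.

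**Conclusion.** The point holds as a cheap improvement with a minor patient-safety benefit. As written, a lactulose subject on one 10g dose who reports more than 4 stools on a survey day is given a dose twice the current one: 20g against 10g, a rise of 10g, and half the assigned 40g. On one 20g packet or on 10g twice daily the message reduces nothing.

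This rests on the protocol text. The REDCap build is not visible and may already branch on dose, but the protocol does not say so. How many subjects will be on one 10g dose is not given, and the situation is probably rare. The documents do not support reading this as a common hazard, as a dose above the assigned one, or as an effect on the trial's outcomes.

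**What to change.** 1. Reword the dosing sentence of the message in 4.3.2, for example: *If you are taking two 20g packets of Kristalose a day, reduce to one packet a day. If you are taking less than that, or have been told to pause or stop, do not increase or restart; please call the study line.* Keep the existing closing line about calling, and keep the staff email alert.
2. State that the dosing text goes only to the lactulose arm. Controls answer the stool question and exit.
3. Put the same condition on the parallel instruction in 4.3.1 item 4, so that the cut to one 20g dose applies only to subjects taking two packets a day.

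The rewording works whether or not staff know of a step-down. It asks for no new information, so it stays within the limits on Twilio content in 7.4.

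The cost is one written amendment with IRB approval (8.4), a longer message and a few more calls to the study line. The extra calls would come mainly from subjects on reduced doses, whom item 4 already tells to call if their stools do not decrease.
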